### **9.2.1. Serious Adverse Events**

An SAE is any AE from this study that results in one of the following:

- death
- initial or prolonged inpatient hospitalization
- a life-threatening experience (that is, immediate risk of dying)
- persistent or significant disability/incapacity
- congenital anomaly/birth defect
- important medical events that may not be immediately life-threatening or result in death or hospitalization but may jeopardize the patient or may require intervention to prevent one of the other outcomes listed in the definition above
- when a condition related to the investigational device (PFS or AI) necessitates medical or surgical intervention to preclude either permanent impairment of a body function or permanent damage to a body structure, the serious outcome of “required intervention” will be assigned.

Study site personnel must alert the Lilly CRP/CP, or its designee, of any SAE as soon as practically possible.

Additionally, study site personnel must alert Lilly Global Patient Safety (GPS), or its designee, of any SAE within 24 hours of investigator awareness of the event via a sponsor-approved method. If alerts are issued via telephone, they are to be immediately followed with official notification on study-specific SAE forms. This 24-hour notification requirement refers to the initial SAE information and all follow-up SAE information.

Although all AEs are recorded in the eCRF after signing informed consent, SAE reporting to the sponsor begins after the subject has signed informed consent and has received IP. However, if an SAE occurs after signing informed consent, but prior to receiving IP, AND is considered Reasonably Possibly Related to a study procedure then it MUST be reported.

Investigators are not obligated to actively seek AEs or SAEs in subjects once they have discontinued from and/or completed the study (the subject summary eCRF has been completed). However, if the investigator learns of any SAE, including a death, at any time after a subject has

been discharged from the study, and he/she considers the event reasonably possibly related to the study treatment or study participation, the investigator must promptly notify Lilly.

Pregnancy (maternal or paternal exposure to IP) does not meet the definition of an AE. However, to fulfill regulatory requirements any pregnancy should be reported following the SAE process to collect data on the outcome for both mother and fetus.

#### **9.2.1.1. Adverse Device Effects**

Any AE believed to be related to an issue with the AI or PFS is considered an adverse device event. These events must be clearly indicated as such in the eCRF, and reported to the sponsor. A PC should also be reported.

For the purpose of this protocol, “unanticipated” adverse device effect means any SAE alleged to be associated or related to the device, and which has been confirmed as such by the sponsor. The SAE relatedness must be clearly indicated as such in the eCRF, and reported to the sponsor within 24 hours of site knowledge of the event. A PC should also be reported.

#### **9.2.1.2. Adverse Events of Special Interest**

The following AEs of special interest will be used to determine the safety and tolerability of LY3074828 injections administered by either PFS or investigational AI in this clinical study.

Adverse events of special interest for LY3074828 are:

- infection
- ISRs
- allergic/hypersensitivity reactions

If infections, ISRs, or allergic/hypersensitivity reactions are reported, sites will provide details on these events as instructed on the eCRF. Investigators will also educate subjects about the symptoms of allergic/hypersensitivity reactions and will provide instructions on dealing with these reactions. A blood sample will be collected when possible for any subject who experiences an AE of allergic/hypersensitivity reaction during the study.

#### **9.2.1.3. Suspected Unexpected Serious Adverse Reactions**

Suspected unexpected serious adverse reactions (SUSARs) are serious events that are not listed in the IB and that the investigator reports as related to IP or procedure. Lilly has procedures that will be followed for the recording and expedited reporting of SUSARs that are consistent with global regulations and the associated detailed guidances.

#### **9.2.2. Complaint Handling**

Lilly collects PCs on IPs and drug delivery systems used in clinical trials in order to ensure the safety of study participants, monitor quality, and to facilitate process and product improvements.

Subjects should be instructed to contact the investigator as soon as possible if he or she has a complaint or problem with the IP or drug delivery system so that the situation can be assessed.

A PFS or AI that is associated with a product quality issue or complaint must be returned to Lilly.

The investigator or his/her designee is responsible for handling the following aspects of the PC process in accordance with the instructions provided for this study:

- recording a complete description of the PC reported and any associated AEs using the study-specific complaint forms provided for this purpose
- faxing the completed PC form within 24 hours to Lilly or its designee.

If the investigator is asked to return the product for investigation, he/she will return a copy of the PC form with the product.

### **9.3. Treatment of Overdose**

For the purposes of this study, an overdose of LY3074828 is considered any dose higher than the dose assigned through randomization.

There is no specific antidote for LY3074828. In the event of an overdose, the subject should receive appropriate supportive care and any AEs should be documented.

Refer to the study drug IB for further details.

### **9.4. Safety**

#### **9.4.1. Laboratory Tests**

For each subject, laboratory tests detailed in [Appendix 2](#) should be conducted according to the Schedule of Activities (Section 2).

Lilly or its designee will provide the investigator with the results of laboratory tests analyzed by a central vendor, if a central vendor is used for the study.

#### **9.4.2. Vital Signs**

For each subject, vital sign measurements (blood pressure, pulse rate, and temperature) should be conducted according to the Schedule of Activities (Section 2). Additional vital signs may be measured during the study if warranted.

Blood pressure and pulse rate should be measured after at least 5 minutes supine.

If orthostatic measurements are required, subjects should be supine for at least 5 minutes and stand for at least 2 minutes.

If the subject feels unable to stand, supine vital signs only will be recorded.

Unscheduled orthostatic vital signs should be assessed, if possible, during any AE of dizziness or posture-induced symptoms.

### **9.4.3. *Electrocardiograms***

For each subject, a single 12-lead digital ECG will be collected according to the Schedule of Activities (Section 2). Electrocardiograms must be recorded before collecting any blood samples. Subjects must be supine for at least 5 minutes before ECG collection and remain supine but awake during ECG collection. Electrocardiograms may be obtained at additional times, when deemed clinically necessary. All ECGs recorded should be stored at the investigational site.

Electrocardiograms will be interpreted by the investigator or qualified designee at the site as soon after the time of ECG collection as possible, and ideally while the subject is still present, to determine whether the subject meets entry criteria at the relevant visit(s) and for immediate subject management, should any clinically relevant findings be identified.

If a clinically significant finding is identified (including, but not limited to, changes in QT/QTc interval from baseline) after enrollment, the investigator will determine if the subject can continue in the study. The investigator, or qualified designee, is responsible for determining if any change in subject management is needed, and must document his/her review of the ECG printed at the time of collection.

Any clinically significant findings from ECGs that result in a diagnosis and that occur after the subject receives the first dose of the IP should be reported to Lilly, or its designee, as an AE via eCRF.

### **9.4.4. *Other Tests***

#### **9.4.4.1. *Tuberculosis Testing***

Subjects will be tested as indicated in the Schedule of Activities (Section 2) for evidence of active or latent TB using the QuantiFERON-TB Gold test. If the test is indeterminate, 1 retest is allowed. If the retest is indeterminate, the subject will be excluded from the study.

Subjects who have had household contact with a person with active TB must be excluded unless appropriate and documented prophylaxis treatment for TB has been completed.

Subjects with any history of active TB are excluded from the study, regardless of previous or current TB treatments.

#### **9.4.4.2. *Injection Duration Assessments***

Injection duration will be measured by a calibrated stopwatch by qualified trained study staff. The duration of injection for the PFS will be defined as the time between when the plunger rod is pressed down and when all of the LY3074828 solution is injected. The duration of injection for the AI will be defined as the time between the first audible click after the injection button is pressed and the last audible click, which indicates that the needle has retracted and the injection is complete.

#### **9.4.4.3. Injection-site Assessments**

Injection site findings (including erythema, induration, pruritus, and edema) will be captured on a separate ISR form, as indicated in the Schedule of Activities (Section 2).

Data from injection site evaluations (including pain) which are recorded as a result of specific questionnaire/s will not be reported as AEs. If the investigator determines that the ISR is clinically significant or if it is an unsolicited event (volunteered by subject), the event will be captured in the subject's eCRF as an AE.

If an ISR is deemed to be an AE, the ISR form will be used to capture specific information about this reaction (eg, degree and area of erythema).

#### **9.4.4.4. Bleeding Assessment**

All injection sites will be observed at the times indicated in the Schedule of Activities (Section 2) by the investigator or designee, and the presence of visible bleeding will be recorded on the eCRF. A bandage may be placed on the injection site after assessment.

#### **9.4.4.5. Injection-site Pain**

Pain measurements will be quantified using the 100-mm validated VAS pain score for all subjects, whether or not they report injection pain. The VAS is a well-validated tool (Williamson and Hoggart 2005) to assess injection-site pain; it is presented as a 100-mm line anchored by verbal descriptors, usually “no pain” and “worst possible pain.” The subject will be asked to rate any pain at the injection site on a scale of 0 to 100 mm on the line immediately (within 1 minute) following the injection and at the time points listed in the Schedule of Activities (Section 2).

### **9.4.5. Safety Monitoring**

The Lilly CP or CRP/scientist will monitor safety data throughout the course of the study.

Lilly will review SAEs within time frames mandated by company procedures. The Lilly CP or CRP will periodically review the following data:

- trends in safety data
- laboratory analytes
- AEs, including monitoring of incidence of any nature of any infections, and ISRs
- PCs

When appropriate, the Lilly CP or CRP will consult with the functionally independent GPS therapeutic area physician, GPS device physician, or GPS clinical research scientist.

#### **9.4.5.1. Hepatic Safety**

If a study subject experiences elevated alanine aminotransferase (ALT)  $\geq 3 \times$  upper limit of normal (ULN), alkaline phosphatase (ALP)  $\geq 2 \times$  ULN, or elevated total bilirubin (TBL)

$\geq 2 \times$  ULN, liver tests (Appendix 4) should be repeated within 3 to 5 days including ALT, aspartate aminotransferase, ALP, TBL, direct bilirubin, gamma-glutamyl transferase, and creatine phosphokinase to confirm the abnormality and to determine if it is increasing or decreasing. If the abnormality persists or worsens, clinical and laboratory monitoring should be initiated by the investigator based on consultation with the Lilly CP or CRP. Monitoring should continue until levels normalize and/or are returning to approximate baseline levels.

Additional safety data should be collected if 1 or more of the following conditions occur:

- elevation of serum ALT to  $\geq 5 \times$  ULN on 2 or more consecutive blood tests
- elevated serum TBL to  $\geq 2 \times$  ULN (except for cases of known Gilbert's syndrome)
- elevation of serum ALP to  $\geq 2 \times$  ULN on 2 or more consecutive blood tests
- hepatic event considered to be an SAE.

#### **9.4.5.2. Monitoring of Hypersensitivity Reactions**

There is a risk of systemic hypersensitivity reactions with any biological agent, including acute anaphylaxis and delayed hypersensitivities to LY3074828. Symptoms and signs that may occur as part of these hypersensitivity reactions include, but are not limited to: fever, chills, joint and muscle pain, rash, itching, urticaria, dizziness, headache, throat irritation, and shortness of breath. Less commonly, life-threatening anaphylactic reactions may occur, which may include vascular collapse and/or respiratory compromise.

All subjects will be closely monitored for signs and symptoms of hypersensitivity reactions following administration of the study drug, and appropriate medical care should be provided. Hypersensitivity reactions will be evaluated by examination of TEAEs and SAEs, and through the use of a follow-up form which will be completed by the investigator. Potential hypersensitivity events will be evaluated by a Lilly CRP based on accepted criteria (Sampson et al. 2006).

### **9.5. Pharmacokinetics**

At the visits and times specified in the Schedule of Activities (Section 2), venous blood samples of approximately 2 mL each will be collected to determine the serum concentrations of LY3074828. A maximum of 3 samples may be collected at additional time points during the study if warranted and agreed upon between both the investigator and sponsor. Instructions for the collection and handling of blood samples will be provided by the sponsor. The actual date and time (24-hour clock time) of each sampling will be recorded.

#### **9.5.1. Bioanalysis**

Samples will be analyzed at a laboratory approved by the sponsor and stored at a facility designated by the sponsor. Concentrations of LY3074828 will be assayed using a validated enzyme-linked immunosorbent assay.

Bioanalytical samples collected to measure IP concentrations will be retained for a maximum of 1 year following last subject visit for the study. During this time, samples remaining after the bioanalysis may be used for exploratory metabolism or exploratory analyses such as bioanalytical assay validation or cross-validation exercises.

## 9.6. Pharmacodynamics

### 9.6.1. Immunogenicity Assessments

Blood samples for immunogenicity testing will be collected to determine antibody production against LY3074828, as specified in the Schedule of Activities (Section 2). Additional samples may be collected if there is a possibility that an AE is immunologically mediated. If additional immunogenicity testing samples are taken, matching PK sample collections will also be required. Immunogenicity will be assessed by a validated assay designed to detect ADAs in the presence of the IP. Antibodies may be further characterized and/or evaluated for their ability to neutralize the activity of the IP.

A risk-based approach will be used to monitor subjects who develop TE-ADAs during and following treatment with LY3074828.

Subjects will have ADA sampling at baseline (predose) and on Days 15, 29, 57, and 85 (see Schedule of Activities [Section 2]).

Subjects who have clinical sequelae that are considered potentially related to the presence of TE-ADA may be asked to return for additional follow-up testing.

Samples will be retained for a maximum of 15 years after the last subject visit, or for a shorter period if local regulations and institutional review boards (IRBs) allow, at a facility selected by the sponsor. The duration allows the sponsor to respond to future regulatory requests related to the IP. Any samples remaining after 15 years will be destroyed.

## 9.7. Genetics

A blood sample will be collected for pharmacogenetic analysis as specified in the Schedule of Activities (Section 2), where local regulations allow.

Samples will not be used to conduct unspecified disease or population genetic research either now or in the future. Samples will be used to investigate variable exposure or response to LY3074828 and to investigate genetic variants thought to play a role in autoimmune and inflammatory diseases. Assessment of variable response may include evaluation of AEs or differences in efficacy.

All samples will be coded with the subject number. These samples and any data generated can be linked back to the subject only by the investigative site personnel.

Samples will be retained for a maximum of 15 years after the last subject visit, or for a shorter period if local regulations and/or IRB impose shorter time limits, for the study at a facility selected by Lilly or its designee. This retention period enables use of new technologies, response

to regulatory questions, and investigation of variable response that may not be observed until later in the development of LY3074828 or after LY3074828 is commercially available.

Molecular technologies are expected to improve during the 15-year storage period and therefore cannot be specifically named. However, existing approaches include whole genome or exome sequencing, genome wide association studies, multiplex assays, and candidate gene studies. Regardless of technology utilized, data generated will be used only for the specific research scope described in this section.

## **9.8. Biomarkers**

This section is not applicable for this study.

## **9.9. Health Economics**

This section is not applicable for this study.

## 10. Statistical Considerations and Data Analysis

### 10.1. Sample Size Determination

Approximately 66 subjects will be enrolled with a target of 60 subjects completing the study (10 completers per treatment).

Data from AMAL (2 x 1-mL doses of 250 mg LY3074828) and AMAE (2 x 1-mL PFS doses of 250 mg LY3074828) studies showed that the geometric coefficient of variation ranged from 55% to 40% for the PK measurements (ie, area under the concentration versus time curve [AUC] from time zero to infinity [AUC(0-∞)], AUC from time zero to time  $t$ , where  $t$  is the last sample with a measurable concentration [AUC(0- $t_{last}$ )], and maximum observed drug concentration [ $C_{max}$ ]). Thus, the geometric coefficient of variation was assumed to be 55% when calculating precision.

A sample size of 60 subjects will provide a precision (ie, half-width of 90% of confidence interval [CI] with a coverage probability of 90%), in log scale, of approximately 0.48 for the geometric means ratio of reference versus test for AUC(0-∞), AUC(0- $t_{last}$ ), and  $C_{max}$ . Equivalently, there is a 90% probability that the distance between the lower limit of the 90% CI and the point estimate of the geometric means ratio is not larger than 38%.

Subjects who are randomized but not administered treatment, or subjects (maximum of 2 subjects per dose regimen arm) that are administered treatment but do not have PK and ADA samples collected up to and including Day 57, may be replaced to ensure that approximately 10 subjects from each treatment arm may complete the study.

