### 10.3. Statistical Analyses

Statistical analysis of this study will be the responsibility of Eli Lilly and Company or its designee.

Pharmacokinetic analyses will be conducted on the full analysis set. This set includes all data from all randomized subjects receiving the dose of LY3074828 with evaluable PK data. Safety analyses will be conducted for all subjects receiving a dose of LY3074828, whether or not they completed all protocol requirements.

Additional exploratory analyses of the data will be conducted as deemed appropriate. Study results may be pooled with the results of other studies for population PK analysis purposes to avoid issues with post-hoc analyses and incomplete disclosures of analyses.

No adjustments for multiple comparisons will be made.

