#### **10.3.2.2. Pharmacokinetic Statistical Inference**

The  $AUC(0-\infty)$ ,  $AUC(0-t_{last})$ , and  $C_{max}$  will be log-transformed and analyzed using a linear fixed-effects model. The model will include device and injection location as fixed effects. The dosing regimen differences between Test and Reference arms will be back-transformed to present the ratios of geometric LS means and the corresponding 90% CI.

The  $t_{max}$  of LY3074828 between Test and Reference arms will be analyzed using a Wilcoxon rank sum test. Estimates of the median difference, 90% CIs, and p-values from the Wilcoxon rank sum test will be calculated.

Additional PK analyses may be conducted if deemed appropriate.

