8.3.2 Pharmacokinetic Statistical Methodology

The AUC(0- ∞), AUC(0- t_{last}), and C_{max} will be log-transformed and analyzed using a linear fixed-effects model. The model will include device and injection location as fixed effects. The differences between the AI (Test) and PFS (Reference) will be back-transformed to present the ratios of geometric least squares (LS) means and the corresponding 90% CI.

Example SAS code:

```
proc mixed data=test alpha=0.1;
  class device location;
  model log_pk = device location / ddfm=kr alpha=0.1;
  lsmeans device / pdiff cl alpha=0.1;
  ods output lsmeans=lsmeans;
  ods output diffs=diffs;
run;
```

The t_{max} of LY3074828 will be analyzed using a non-parametric method. Estimates of the median difference between AI (Test) and PFS (Reference), 90% CIs, and p-values from the Wilcoxon rank sum test will be calculated.

The above analyses will also be repeated for each location separately.

Additional PK analyses may be conducted if deemed appropriate.

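### The 0.48 log half-width (38%) credited to 60 subjects is the precision of one single-location 10 v 10 comparison; the planned device + location model gives about 0.25 (22%), which neither document states.

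*Protocol*

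**What the plan says.** Protocol 10.1 opens with a "target of 60 subjects completing the study (10 completers per treatment") and assumes a geometric CV of 55%, the upper end of the 40% to 55% seen in two earlier studies. It then says "A sample size of 60 subjects will provide a precision", defined as the half-width of a 90% CI attained with 90% probability, "in log scale, of approximately 0.48 for the geometric means ratio of reference versus test". It restates this as a lower limit no more than 38% below the point estimate. SAP 7 repeats the text. Neither section names an injection location, a number per group or the model behind the figure.

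On the analysis, Protocol 10.3.2.2 says of the log-transformed AUCs and Cmax: "The model will include device and injection location as fixed effects". It adds no interaction term, and continues: "The dosing regimen differences between Test and Reference arms will be back-transformed". SAP 8.3.2 has the same model and is more specific about the contrast: "The differences between the AI (Test) and PFS (Reference) will be back-transformed", with the code line "lsmeans device / pdiff cl alpha=0.1". SAP 8.3.2 then adds that the analyses are repeated within each location. Protocol 10.3.2.2 does not mention that repeat.

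**The concern.** The precision sentence has all 60 subjects as its basis and a single reference-versus-test ratio as its target. The main model does produce a single AI:PFS ratio from all 60, so a reader will take 0.48 as the precision of that ratio. If the figure instead belongs to a two-arm comparison of 20 subjects, the only stated justification for the sample size describes a secondary repeat analysis. The main PK contrast, which carries the PFS-to-autoinjector bridging purpose, then has no stated precision.

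**Working it through.** **Inputs**
- Geometric CV 55%, with 40% as the lower end of the range (Protocol 10.1).
- 60 completers, 10 in each of six arms (Protocol 10.1), hence 30 AI and 30 PFS.
- 90% two-sided CI and 90% probability of not exceeding the half-width (Protocol 10.1).
- Additive device + location model (Protocol 10.3.2.2), with a device contrast and a by-location repeat (SAP 8.3.2).

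**Formulas**
- Log-scale SD: σ = √ln(1 + CV²) = √ln(1 + 0.55²) = 0.5141.
- Half-width with 90% assurance, n per side: w = t(0.95, df) × σ × √(2/n) × √(χ²(0.90, df)/df).
- Ratio scale: lower limit 1 − e^(−w) below the estimate, upper limit e^w − 1 above it.

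**The plan's figure, reproduced.** One location analysed alone: n = 10, df = 20 − 2 = 18.
- σ√(2/10) = 0.2299; t = 1.7341; √(25.989/18) = 1.2016.
- w = 1.7341 × 0.2299 × 1.2016 = **0.479**.
- 1 − e^(−0.479) = 38%; e^0.479 − 1 = 61%.

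Both stated figures, 0.48 and 38%, come out.

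**The planned main model.** Device contrast: n = 30, df = 60 − 4 = 56 (intercept, one device and two location parameters).
- σ√(2/30) = 0.1327; t = 1.6725; √(69.919/56) = 1.1174.
- w = 1.6725 × 0.1327 × 1.1174 = **0.248**.
- 1 − e^(−0.248) = 22%; e^0.248 − 1 = 28%.

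The ratio of the two half-widths is 0.479/0.248 = 1.93. A simulation of 40,000 trials with six arms of 10 gave 90th percentiles of 0.478 (one location analysed separately) and 0.248 (device contrast). In a second simulation of the 30 v 30 contrast on 56 df, the half-width was at most 0.48 in essentially every draw, against the stated 90%.

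**Other readings and sensitivity**

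| Contrast | n v n | df | w |
|---|---|---|---|
| One location, device-by-location model on all 60 | 10 v 10 | 54 | 0.431 (35% below, 54% above) |
| One location alone, CV 40% | 10 v 10 | 18 | 0.359 |
| Device contrast, CV 40% | 30 v 30 | 56 | 0.186 |
| One location alone, 9 per arm (assumed) | 9 v 9 | 16 | 0.513 |
| Device contrast, 9 per arm (assumed) | 27 v 27 | 50 | 0.264 |
| One location alone, 11 per arm (assumed) | 11 v 11 | 20 | 0.451 |
| Device contrast, 11 per arm (assumed) | 33 v 33 | 62 | 0.235 |

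The 9 and 11 per arm rows are there because Protocol 10.3 says "Pharmacokinetic analyses will be conducted on the full analysis set", meaning dosed subjects with evaluable PK data, who need not number exactly 10 per arm. The gap between the two contrasts stays at nearly a factor of two throughout. Of the contrasts computed with 60 subjects at CV 55%, only the separate single-location analysis gives 0.48.

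**The case against.** The best defence is that 0.48 was always meant arm against arm. Test and Reference are labels for six separate arms, the SAP treatment table lists six treatments, and the opening sentence of each sample-size section gives completers per treatment. Protocol 10.3.2.2 also speaks of differences between dosing regimens. On that reading the sentence is true: 60 completers are what supply 10 per arm, and each Test/Reference pair then has a half-width of 0.48. The by-location analysis is planned in the SAP, comparing devices at each site is a purpose of the design, and quoting the least precise planned comparison is a cautious choice. No equivalence margin or precision target depends on the pooled figure.

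Much of this stands. The number is correctly calculated, the pairwise reading explains its origin, and a reader who applies it to the pooled ratio only understates the precision. It does not make the text right as written. Neither sample-size section says the figure is pairwise. The additive model estimates one device ratio common to the three locations, and the SAP code requests exactly that ratio. Even a 10 v 10 contrast using the variance from all six arms would give 0.431. The analysis that does give 0.48 appears only as a repeat, and only in the SAP.

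**Conclusion.** The concern holds, at minor severity. The arithmetic behind 0.48 and 38% is sound, but the figure is attached to the wrong contrast. For the overall AI:PFS ratio from the planned model, 60 subjects give about 0.25 on the log scale (22% below, 28% above), roughly half the stated half-width. The 0.25 rests on a CV of 55%, 10 evaluable subjects in every arm and a common device effect across locations, as the additive model itself assumes. Enrolment, the analysis and all decision rules are unaffected.

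**What to change.** Replace the precision sentence in Protocol 10.1 and SAP 7 with wording such as:

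> With 60 evaluable subjects (10 per arm) and a geometric CV of 55%, the 90% CI half-width (with 90% probability) is about 0.25 in log scale for the overall AI:PFS ratio from the device + location model, assuming a common device effect across locations (lower limit 22% below and upper limit 28% above the estimate). For a ratio at a single location analysed separately (10 v 10), it is about 0.48 (38% below, 61% above).

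The cost is one sentence in each of two documents, with no change to enrolment or analysis.
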